### Stratified Randomization Procedure and Masking

#### Sequence Generation

We used a two-stage procedure for randomization. First, participants eligible for recruitment were stratified into two groups based on the presence or absence of symptoms of anxiety or depression reported at any point between December 2022 and December 2023. Second, participants in both strata were randomized to one of the three intervention arms upon being enrolled. Thus, participants were randomized separately according to symptoms of anxiety or depression.

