#### Secondary Outcome: Vaccine Willingness at 4 Weeks

At the 4-week survey, participants who had not received an additional dose of the vaccine were asked, "How willing are you to receive another COVID-19 vaccine dose?" with response options: "Very willing", "Somewhat willing", "Not willing", or "Don't know". Only participants who responded 'Very willing' were defined as vaccine willing.

Pre-trial vaccine willingness. After enrollment, but before randomization into an intervention arm, participants were asked, "How willing are you to receive another COVID-19 vaccine dose?" with response options: "Very willing", "Somewhat willing", "Not willing", or "Don't know".

Post-trial vaccine willingness: Immediately after the intervention, participants were asked: "How likely are you to make time to get a vaccine in the next month?" with response options: "Very likely," "Somewhat likely," "Not likely," and "Don't know/not sure." They were also asked:

"Are you planning to make an appointment to get the COVID-19 vaccine in the next month?" with options: "Already made an appointment", "Planning", "Not planning", "Don't know/not sure". These questions were asked again in the 4-week follow-up survey, but only among participants who had not received an additional vaccine dose during that time. For participants with missing follow-up data (N=56), responses from the immediate post-intervention survey were used as imputed values.

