### Statistical Analysis Plan

All statistical analyses were performed blind to study arm allocation. We present frequencies and summaries of characteristics by treatment assignment. Standardized mean differences (SMD) were reported. For post-randomization characters, Chi-squared or Fisher's exact tests were used to compare proportions.

Primary analyses were performed under the intention-to-treat principle, including all participants who underwent randomization. Strict intention-to-treat analysis is hard to achieve for two reasons: missing outcomes for participants and protocol non-adherence. For the primary analysis, we used multiple imputation for those lost to follow-up at some point after randomization (as recommended by the CONSORT statement), which has the benefit of including all randomized participants. As a sensitivity analysis, we assessed loss to follow-up assumptions under (1) multiple imputation and (2) protocol non-adherence (see Appendix).

For the primary outcome, we generated risk ratios using a robust Poisson regression model and generated risk differences. For the secondary outcome of vaccine willingness, we generated risk ratios using a Poisson regression model. The model for the overall effect estimation included the randomization arms and a term for the presence or absence of symptoms of anxiety or depression reported between December 2022 and December 2023. For an Intention to Treat (ITT) analysis of a stratified randomized trial, adjustment is recommended for the stratification variable  on the principle that the analysis should follow the design.

To assess the effect of the intervention according to symptoms of anxiety or depression, we restricted them to subsets with or without symptoms. The stratified models included only randomization arms as the independent variable. Similarly, post-hoc stratification analyses for the primary and secondary outcomes were conducted separately among subsets of participants based on the presence or absence of the post-hoc stratification factors (susceptibility to severe

COVID-19, worry about COVID-19 and pre-trial perceptions of vaccine efficacy). The model included randomization arms and accounted for the presence or absence of symptoms of anxiety or depression.

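### Vaccine willingness was measured before randomisation with the same item as the 4-week secondary outcome, but no listed outcome model adjusts for it; the cost is precision, of a size the documents do not fix

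*Combined protocol and SAP*

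**What the plan says.** Under Secondary Outcome: Vaccine Willingness at 4 Weeks, the outcome is one question with four response options, scored as Very willing against everything else. The same section describes pre-trial willingness with identical wording and options, and gives its timing: "After enrollment, but before randomization into an intervention arm, participants were asked".

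The Statistical Analysis Plan gives three forms of outcome model:

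- Overall effect: "The model for the overall effect estimation included the randomization arms and a term for the presence or absence of symptoms" of anxiety or depression.
- Within symptom strata: "The stratified models included only randomization arms as the independent variable".
- Post-hoc subsets: "The model included randomization arms and accounted for the presence or absence of symptoms of anxiety or depression".

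Pre-trial willingness is in none of them, and it is not one of the three post-hoc stratification variables. The reason given for the stratum term is that the analysis should follow the design. The listed sensitivity analyses (complete case, inverse probability weighting, per-protocol, multiple imputation) address loss to follow-up and adherence. Details are left to Appendices B and C, which are not in the text available for this review.

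**The concern.** A baseline measurement of the outcome itself is usually among the strongest predictors of its later value. Here it has already been collected, on the same scale. Following the design is a good reason to include the stratum term, but no reason to leave the baseline outcome out.

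At stake is the width of the intervals for the arm comparisons. Chance imbalance between arms in baseline willingness is part of the same loss: it is the noise that adjustment would remove. The secondary outcome is the main case, because the covariate is the same item. For the primary outcome the gain depends heavily on how common vaccination was.

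**Working it through.** **No figure to reproduce.** The documents state no total sample size, power, significance level, target effect, outcome rate or baseline willingness distribution. The inputs below are therefore assumptions, apart from the item, its timing and the model terms.

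**Formula.** For a log-link model with robust variance at a risk ratio of 1, the variance of the log risk ratio is proportional to p(1−p) without the covariate and to E[μ(1−μ)] with it. Here p is the overall outcome probability and μ the probability at each baseline level. The gain in effective sample size is

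gain = p(1−p) / E[μ(1−μ)] − 1.

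**Assumed baseline distribution:** very willing 20%, somewhat 35%, not 35%, don't know 10%. Missing data and any effect of the symptom stratum are ignored.

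**Worked case (secondary, moderate).** Very-willing rates at 4 weeks by baseline level: 55/20/3/10%.

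- p = 0.2×0.55 + 0.35×0.20 + 0.35×0.03 + 0.1×0.10 = 0.2005, so p(1−p) = 0.1603.
- Four categories: 0.2×0.2475 + 0.35×0.16 + 0.35×0.0291 + 0.1×0.09 = 0.1247. Gain = 0.1603/0.1247 − 1 = 28.6%.
- Binary coding: the rate among the others is 0.0905/0.8 = 0.1131, giving 0.2×0.2475 + 0.8×0.1131×0.8869 = 0.1298. Gain = 23.5%.

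The other rows use the same steps:

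| Outcome, association | Rates by baseline level (%) | p | Gain, four-category | Gain, binary |
|---|---|---|---|---|
| Secondary, weak | 40/20/5/10 | 0.178 | 12.6% | 9.3% |
| Secondary, moderate | 55/20/3/10 | 0.201 | 28.6% | 23.5% |
| Secondary, strong | 70/15/2/5 | 0.205 | 65.6% | 60.6% |
| Primary, weak | 10/5/2/4 | 0.049 | 1.8% | 1.5% |
| Primary, moderate | 15/5/1/3 | 0.054 | 5.3% | 4.7% |
| Primary, strong | 20/3/0.5/1 | 0.053 | 12.2% | 12.0% |

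With the primary rates divided by five (about 1% uptake), the four-category gains are 0.3/1.0/2.1%. With them tripled (about 15% uptake) they are 6.3/20.7/58.4%. The last figure needs 60% of the very willing to be vaccinated within four weeks, and nothing in the documents supports that.

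**Check with missing data.** Trials were simulated with 56 outcomes missing at random, 20 imputations, robust Poisson models and Rubin's rules, for N of 450, 900 and 1200 and risk ratios of 1 and 1.35. The count of 56 is the plan's number with missing follow-up; the mechanism is assumed. Uptake was set equal across arms. Secondary gains over all these settings were:

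| Association | Binary | Four-category |
|---|---|---|
| Weak | 5.1–9.9% | 6.6–14.2% |
| Moderate | 17.1–27.0% | 20.0–34.6% |
| Strong | 44.0–70.0% | 49.0–74.5% |

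Using the item in the imputation model but not in the outcome model gained 0.0–5.6%.

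**Check on bias.** In a separate simulation with every randomised participant analysed (300 per arm; 20% very willing; rates 60% and 5%), the mean log risk ratio was 0.257 without the covariate and 0.258 with it, against a true 0.262. Under no effect it was −0.005 and −0.002.

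**The case against.** **The plan is valid as written.** Adjusting for the stratification factor alone is a defensible, reasoned choice, and omitting an optional prognostic covariate contradicts nothing in the documents. This stands, and it limits the point to a suggested improvement.

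**It is too late.** The plan describes a completed analysis. A model added now is post hoc and cannot recover design-stage power. This also stands.

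**The size is assumed.** It is: confidence attaches to the omission, not to the percentages.

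**The appendices may use the item.** They may, for imputation or weighting. That is not adjustment of the arm comparison, and the simulation found that imputation use alone recovered little.

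The documents do not support four stronger readings that a reader might infer:

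- *The omission biases the results.* It does not; randomisation protects the unadjusted comparison.
- *The secondary comparison is therefore free of bias.* This does not follow either. At 4 weeks only "participants who had not received an additional dose of the vaccine were asked", and the plan does not say how vaccinated participants enter the analysis. If they are dropped, an arm that raises uptake changes who remains. In an illustration with no true effect on willingness and uptake raised 1.5- to 2-fold, the crude risk ratio ran from about 0.99 to 0.86. Adjustment restored 1.00 only because willingness was assumed to be the sole common cause. This is a separate issue.
- *The secondary model used the wrong variance.* The plan says "For the primary outcome, we generated risk ratios using a robust Poisson regression model and generated risk differences", then "For the secondary outcome of vaccine willingness, we generated risk ratios using a Poisson regression model". The missing word may be mere abbreviation. It is a separate reporting query.
- *The timing is contradictory.* Sequence Generation says "participants in both strata were randomized to one of the three intervention arms upon being enrolled". That is compatible with a question asked just before assignment.

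**Conclusion.** The point holds as an optional improvement. The text shows plainly that a baseline measure of the secondary outcome was collected before randomisation and appears in no listed outcome model. The consequence of that omission is lost precision, not bias.

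The secondary outcome is where it matters: a gain in effective sample size of roughly 13%, 29% or 66% by strength of association, with four-category coding, no missing data and a risk ratio of 1. For the primary outcome it is about 2% to 12% at 5% uptake, less if vaccination was rarer and more if it was commoner. All of this rests on the assumed 20% very willing at baseline and the assumed rates by level. The study team holds the real values and can settle the size directly.

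**What to change.** Keep the current models as the reported analyses. Add versions adjusted for pre-trial willingness, labelled post hoc and supportive, chiefly for the secondary outcome:

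- Confirm from the survey flow that the item preceded assignment.
- Use binary coding (Very willing against other) in symptom strata, in post-hoc subsets and for the primary outcome. Four categories are workable for the overall secondary model if no level is empty of events.
- Use Poisson models with robust variance, fitted in each imputed dataset and pooled. If the imputation model does not include the item, re-impute first.
- Obtain adjusted risk differences by standardising the model's predictions.
- State whether the imputation and weighting models use the item, and that such use does not replace outcome-model adjustment.

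Handle separately the variance method of the current secondary model and the restriction of the 4-week item to participants not vaccinated since the intervention. Adjustment does not fully remove any selection from that restriction.

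The cost is a modest rerun, possibly with re-imputation, and some plan text; no new data are needed. The downsides are post hoc status and unstable fits in sparse strata. In a simulated stratum of 360, four-category coding met a response level with no events in at least one imputed dataset in 4–27% of trials (secondary) and 33–88% (primary at 5% uptake). Binary coding failed in 0% and 0.6–1.7%, against 0.5–1.6% for the unadjusted primary model. Log-binomial regression is not a safe substitute: it failed to converge in 55% of trials in one strong-association case.

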### **Intervention and Control Conditions**

Participants viewed one of three one-minute videos. The video content of the experimental arms was developed using formative mixed-methods research, including a pre-trial survey with CHASING COVID participants on vaccine perceptions and qualitative interviews with participants reporting anxiety or depression in earlier questionnaires. This process revealed a common concern about vaccine effectiveness as a broader "meta-narrative" across participants. Additionally, those with anxiety or depressive symptoms were more likely to cite not "making time" as a reason for being behind on vaccination- a theme later incorporated into the CBT-kernels condition.

Specifically: 1) The inoculation video addressed concerns about vaccine effectiveness, focused on bolstering resistance to mis/disinformation. 2) The CBT-kernels video focused on addressing barriers to vaccination, specifically making time to get vaccinated. It focused on cognitive reframing—highlighting how individuals might selectively focus on information that reinforces vaccine-related anxiety, challenging those beliefs, and encouraging problem-solving around making time to get vaccinated. 3) The standard public health messaging arm was a brief video adapted from existing public health PSAs, with no inoculation or CBT-kernels elements.

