## Attitudinal inoculation to increase vaccination among adults with anxiety or depression RF1MH132360

### Study Protocol and Statistical Analysis Plan May 2, 2025

After receiving the brief digital intervention, participants received two reminders to get vaccinated by text or email on the first and third days after completing the baseline assessment. Messages were tailored to each arm and included a link to a COVID-19 vaccine locator. Their content can be found in Appendix A.

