Lastly, the validity of an ITT effect estimate requires correct adjustment for selection bias due to differential loss-to-follow-up and missing outcome data. We used multiple imputation for loss-to-follow-up and missing data, hence conducting stratified analyses to assess effect modification rather than relying on interaction terms, as standard interaction testing isn't directly applicable to imputed datasets. Details on imputation methods are included in Appendix C. Methods for sensitivity analyses can be found in Appendix B. A series of sensitivity analyses were conducted to address assumptions related to loss to follow-up and protocol adherence, including complete case analysis, inverse probability weighting, perprotocol analysis for participants fully adhering to the intervention, and multiple imputation for missing outcomes, with consistent results observed across primary and secondary outcomes.

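### Multiple imputation is given as the reason to avoid interaction terms, but it only requires pooling them; as described, the plan never estimates the difference between strata

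*Combined protocol and SAP*

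**What the plan says.** The Statistical Analysis Plan uses multiple imputation for missing outcomes and gives this as the reason for "conducting stratified analyses to assess effect modification rather than relying on interaction terms, as standard interaction testing isn't directly applicable to imputed datasets". The method is set out earlier in the same section: "To assess the effect of the intervention according to symptoms of anxiety or depression, we restricted them to subsets with or without symptoms", and "The stratified models included only randomization arms as the independent variable". The overall model has arm and symptom main effects and no product term. The three post-hoc factors (susceptibility to severe disease, worry, perceived efficacy) are also handled by separate subset fits, with a symptoms term added.

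For the primary outcome, "we generated risk ratios using a robust Poisson regression model and generated risk differences", so both scales are in use. The sensitivity analyses listed in the final paragraph include analyses without imputation: "including complete case analysis, inverse probability weighting".

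Symptom status is the randomization stratifier. The title reads "Attitudinal inoculation to increase vaccination among adults with anxiety or depression". Under Intervention and Control Conditions, the difficulty of finding time, which formative work found was named more often by people with symptoms, is described as "a theme later incorporated into the CBT-kernels condition". No section states a hypothesis that the effect is larger in people with symptoms.

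**The concern.** Effect modification is a difference between stratum effects. To assess it one needs an estimate of that difference with its uncertainty. Two sets of separate fits give valid effects within each stratum but not that quantity, and the reason offered for stopping there is a mistaken inference from multiple imputation.

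The consequence is for interpretation. Given only stratum results, readers tend to compare significance labels, and labels can disagree when the true effects are equal. The design invites the comparison, because one video took up a barrier cited more often by people with symptoms.

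**Working it through.** **Inputs.** From the documents: three arms at 1:1:1, so arm by symptoms has 2 df; robust Poisson for the primary outcome; 56 participants with missing follow-up (stated for the willingness items under Secondary Outcome). The documents give no sample size, event rate, symptom share or power, so there is no stated figure to reproduce. All sizes and rates below are assumptions.

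**1. Can the interaction be pooled?** With M imputed datasets, estimates Q_m and variances U_m, Rubin's rules give the mean of Q_m with variance T = Ū + (1 + 1/M)B, where B is the between-imputation variance. Nothing in this depends on whether Q is an arm effect or a product term. For k = 2 coefficients the pooled Wald statistic is D1 = Q̄′Ū⁻¹Q̄ / [k(1 + r)], with r = (1 + 1/M) tr(BŪ⁻¹)/k, referred to an F distribution.

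**2. Is the product term anything new?** In one simulated dataset, a joint robust Poisson model gave interaction coefficients −0.0307 and −0.3920 (SE 0.2933 and 0.2639). The differences of the separately fitted stratum log risk ratios, and their standard errors, were identical to all printed digits. The contrast can therefore be formed from fits the plan already makes.

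**3. How often do labels disagree when effects are equal?** For independent strata with powers p1 and p2, P(exactly one significant) = p1(1 − p2) + p2(1 − p1).
- 80% and 80%: 0.8 × 0.2 × 2 = 32%.
- 50% and 50%: 0.5 × 0.5 × 2 = 50%.
- 30/70 split, 80% power in the larger stratum: noncentrality 2.80 in the larger and 2.80 × √(0.3/0.7) = 1.83 in the smaller, so power is 45% in the smaller. Then 0.80 × 0.55 + 0.45 × 0.20 = 53%.

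**4. Simulation with imputation.** N 500, 800 or 1200; symptom share 30% or 50%; 56 expected missing; 20 imputations within arm and stratum; 4,000 runs per scenario; no true modification; one video against control. The first two result columns are at a risk ratio of 1.5 in both strata. Log-risk-ratio results at every risk level exclude runs with an empty cell.

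| Control risk | Labels differ | Pooled 1-df interaction test rejects | Runs with an empty cell | 95% CI factor, ratio of risk ratios | 95% CI half-width, difference in risk differences |
|---|---|---|---|---|---|
| 15–30% | 25–55% | 3.7–5.6% | 0–0.3% | 1.5–3.5 | 10–24 points |
| 5% | 7–26% | 1.6–4.6% | 0–31% | 3.2–11 | 6–12 points |
| 2% | 0.3–8% | 0–2.9% | 5–87% | 7–25 | 4–8 points |

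The CI factor is the number by which the ratio is multiplied and divided. The pooled difference in risk differences rejected a true null in 4.4–6.0% of runs at 5–30% risk and 2.5–5.3% at 2%. A separate run of the 2-df D1 test (N 600 or 1200, 20% risk, risk ratio 1.0 or 1.5) rejected in 3.7–5.8%. With no effect in either stratum, labels differed in 8.7–9.5% of those runs, close to the 2 × 0.05 × 0.95 = 9.5% expected.

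The missing count matters little. At N 800 and 15% risk, going from 1 to 160 missing moves the CI factor from 2.3–2.5 to 2.5–2.8.

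**5. Power of the contrast.** Take an interaction as large as a stratum effect that has 80% power.
- Equal strata: noncentrality 2.80/√2 = 1.98, power 51%.
- 30/70 split: 2.80/√(1 + 0.7/0.3) = 1.53, power 34%, if the effect is sized to the larger stratum; 2.80/√(1 + 0.3/0.7) = 2.34, power 65%, if sized to the smaller.

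**The case against.** The quoted sentence is true in a narrow sense: p-values or likelihood-ratio statistics from single imputed datasets cannot simply be averaged. The fault lies in inferring omission from that. The source cited for the sentence was not available and is not relied on here.

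Appendices A to C were not available and could contain a contrast. That limits the statement about absence to the available text. It does not rescue the reasoning, and the reason does not arise in the complete case and inverse probability weighted analyses.

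The title and the stratified randomization also fit an interest in the effect within the symptom stratum, which the separate fits estimate validly. But the plan itself names effect modification as the aim.

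The harm is conditional. The documents draw no subgroup conclusion and do not plan to compare labels. Disagreement is frequent only when there is a real effect and outcomes are reasonably common; at 2% risk it is at most 8%. Those limits stand.

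Two practical points also stand. If the imputation model lacks an arm-by-symptoms term, the data must be re-imputed. And four factors by two outcomes make eight 2-df tests, with a chance of 1 − 0.95⁸ = 34% of at least one false positive if they were independent.

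**Conclusion.** The concern holds. The stated reason for avoiding interaction terms is wrong as an inference, and the analysis as described does not deliver the assessment of effect modification that the plan sets itself. The primary intention-to-treat result and the stratum risk ratios are not affected.

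Confidence is high on the pooling argument, which is algebra. The absence of a contrast is subject to the unseen appendices. The size of the interpretive risk depends on assumed inputs: under equal effects it ranges from under 1% label disagreement at 2% control risk to 55% at 15–30%. The pooled test stayed near or below its nominal 5% throughout.

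**What to change.** Correct the sentence in the final paragraph of the Statistical Analysis Plan: imputation requires the interaction to be pooled, not omitted. Then:

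- In each imputed dataset, fit arm, symptoms and arm by symptoms with robust standard errors for both outcomes (the plan says robust only for the primary one).
- Use an imputation model that allows arm by symptoms, or impute within arm and stratum. Without this the pooled interaction is biased toward none. Appendix C may already do so.
- Report, for each video against control, the pooled ratio of risk ratios with 95% CI, and the 2-df pooled Wald test.
- For the primary outcome, also report the difference in risk differences with 95% CI, because modification depends on scale. A common risk ratio of 1.5 at assumed control risks of 10% and 20% gives risk differences of 5 and 10 points.
- Treat the three post-hoc factors likewise, keeping the symptoms adjustment. Label all of these contrasts as added after data collection and the post-hoc ones as exploratory, with emphasis on intervals given the number of tests.
- Keep the stratum risk ratios as description.

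If no contrast is reported, make no claim of a differential effect.

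The cost is one sentence and a few lines of code on the existing imputed data, plus re-imputation if the current model lacks the interaction. The drawback is imprecision. At 2% risk the ratio of risk ratios is close to uninformative and often cannot be computed, while the difference in risk differences stayed estimable in over 99% of simulated runs.
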